1.0 BACKGROUND AND RATIONALE

1.1 Study Synopsis

In this study, we propose to test the efficacy of a couple-focused, web-based tailored prostate cancer symptom management program (PERC) in a randomized clinical trial. We will use a two-group (**PERC versus NCI website**) randomized controlled design and collect data at baseline (T1) and 4 (T2), 8 (T3), and 12 months (T4) among 800 patients (400 patient – partner dyads) completing initial treatment for localized prostate cancer and their intimate partners.

1.2 Background

Over 180,000 new cases of prostate cancer will be diagnosed in 2016,¹ and 92% will have localized or regional disease.² Despite a favorable five-year relative survival at 100%,³ men with localized prostate cancer experience serious prolonged side effects after treatment with curative intent,⁴ including urinary, sexual, bowel, and hormonal symptoms; emotional distress; and general symptoms, e.g., pain, fatigue, and sleep disturbance; and change in body image, all of which impair their quality of life (QOL).⁴ For men in an intimate relationship, these symptoms disrupt couples' intimacy and relationships;⁵⁻⁸ the symptoms' adverse effects on their intimate partners' QOL may be greater than the effects on patients' own QOL.^{9,10}

1.3 Purpose and Rationale

Despite these challenges the patients and their partners face, as well as national guidelines on cancer survivorship from the Institute of Medicine (IOM)¹¹ and the American Cancer Society (ACS),⁴ management of negative treatment effects remains the most unaddressed supportive care need for cancer patients and their families.¹²⁻¹⁴ Available in-person interventions are expensive to deliver and inconvenient for patients with prostate cancer and their intimate partners to attend together. Existing web-based programs often are not couple-focused, lack theory guidance, are not tailored to patient and partner needs, and are tested in studies with major methodological flaws. (Note: "partner caregivers/intimate partners" are replaced by the term "partners" sometimes in this proposal due to space limitation).

To address the unmet care needs for survivors and their partners, [name] (PI) led an interdisciplinary team to develop and test the usability and feasibility of a tailored, couple-focused mHealth intervention called **Prostate Cancer Education & Resources for Couples (PERC)**. Guided by an adapted Stress and Coping theoretical framework, PERC was developed with contribution of stakeholders (patients, partners, and oncologic care providers),¹⁵ and findings from efficacious interventions with cancer patients and partners^{16,17} and empirical evidence.^{4,16-19} PERC aims to improve QOL for both patients and partners by enhancing positive appraisals of illness and boosting self-efficacy, social support from multiple sources, and healthy behaviors for symptom management. PERC uses mHealth technologies to dramatically increase couples' accessibility to post-treatment supportive care whenever and wherever they feel comfortable accessing it.¹⁵ The three main components of PERC are: (1) online educational modules to provide information and skills training, and facilitate dyadic support; (2) a moderated online Forum to facilitate professional and peer support; and (3) a Resource Toolbox to provide additional local and national resources, and easy access to useful information and tools to improve symptom management.

We tested and further refined PERC in two pilot studies. Patients and their partners were enthusiastic about and satisfied with the PERC intervention. They found the website easy to use, and it provided quality information that improved their symptom management and QOL.¹⁵ Based on our preliminary results, we believe that the refined PERC mHealth intervention is ready for efficacy testing in a randomized clinical trial.

2.0 STUDY OBJECTIVES/AIMS AND ENDPOINTS

In this randomized controlled trial, we will examine the efficacy of a couple-focused, web-based tailored prostate cancer symptom management program (PERC). We will use a two-group (**PERC versus NCI website**) randomized controlled design and collect data at baseline (T1) and 4 (T2), 8 (T3), and 12 months (T4) among 800 patients (400 patient - partner dyads) completing initial treatment for localized prostate cancer and their intimate partners.

2.1 Primary Objective: Assess the efficacy of PERC for improving QOL (total score and subscale scores of the physical, social, mental, and functional domains) among patients and their intimate partners.

H 1: Patients and their intimate partners randomized to PERC will report a larger increase in QOL scores (as assessed by the Functional Assessment of Cancer Treatment, FACT-G) than those randomized to the control group (usual care plus the National Cancer Institute prostate cancer website, the NCI website) at 4, 8, and 12 months post-baseline

2.1.1 Our primary outcome is the total QOL score, and each of the QOL subdomains are secondary outcomes.

2.2 Secondary Objectives: Test the effects of PERC on symptom appraisals and coping resources.

H 2: Patients and their intimate partners randomized to PERC will report greater improvement in secondary outcomes, positive appraisals of illness and coping resources, i.e., self-efficacy in symptom management, greater social support, and use of more healthy behaviors, at follow-ups than those randomized to the control group.

2.3 Exploratory Objective: Explore whether patients' race/ethnicity, education, type of cancer treatment, and couples' relationship quality at baseline moderate the effects of PERC on patient and partner QOL at follow-ups.

3.0 PATIENT ELIGIBILITY

3.1 Inclusion Criteria

The eligible patients must

- (1) be between 40 and 75 years old.
- (2) be within 4 months after completing initial treatment for localized prostate cancer as confirmed by patient and biopsy pathology report) with curative intent, i.e., surgery or radiotherapy +/- hormonal treatment;
- (3) have no previous cancer history within the past 2 years and not currently in treatment for cancer, or have a concurrent cancer (excluding non-melanomatous skin cancer);

- (4) experience prostate cancer-specific and/or general symptoms;
(5) have a partner who is willing to participate.

The eligible partners must

- (1) be 18 years or older
- (2) be identified as the partner by the patient
- (3) not have been diagnosed with cancer or receiving treatment for cancer within the past 12 months (non-melanomatous skin cancer diagnosis/treatment is diagnosis/treatment is acceptable) so that couples can focus their efforts on managing prostate cancer.

[figure not shown]
3.2 Exclusion Criteria

Patients and their partners will be excluded from the study if they:

- Do not read and speak English (evidenced by their understanding and responses to screening questions and self-reported ability to read English);
- Have cognitive impairment (assessed by the Short Portable Mental Status Questionnaire).

4.0 STUDY PLAN

4.1 Schema

4.2 Duration of Study

In this 5-year RCT, participants randomly assigned to the PERC group (the experimental group) will have access to the mHealth intervention titled Prostate Cancer Resources for Couples (PERC). The PERC users will have the chance to “meet” with a nurse educator via telephone and/or zoom video conferencing every 3-5 weeks for approximately 16-20 weeks. These will be scheduled via phone calls, emails or secure text messages (see section 4.3 below) to occur at these approximate time points: 1 week after completing the Baseline Survey (T1), and then three more at 3-5 week intervals for a total duration of 16 weeks. These intervals are flexible so that the patient/partner schedules can be accommodated and allow all 4 meetings to occur prior to the T2 survey. At the first intervention the Health Educator will describe how best to use the website and assist the couple to explore its features and different modules to manage post treatment symptoms whether emotional or physical. Participants will be encouraged to contact the Health Educator should they have questions.

Participants will also be given an option to utilize a tablet provided by the research team. If the participant does not have internet access, a Verizon jet pack (hot spot), along with user guide, will also be provided to the participant so that the surveys can be accessed. The tablet and jet pack will be returned when study participation is complete.

Content for subsequent interventions will be based on symptoms either member of the dyad is experiencing, making use of the PERC website for assistance in symptom

management. Dyads in the experimental group will have unlimited access to the PERC website after the final planned intervention.

Participants in the control group will have unlimited access to the NCI prostate cancer website. The Health Educator will have one phone meeting with them and their partners and answer any questions they have on accessing and navigating the NCI website. The control group will then receive emails and text messages approximately every 3-5 weeks until sixteen weeks to remind them to access the NCI website. As above, these intervals are flexible to allow for 3 reminders to be sent prior to the T2 Survey.

All participants will complete 3 follow-up surveys at around 4 (T2), 8 (T3), and 12 (T4) months post Baseline survey (T1)

4.3 Study Details

We plan to recruit 400 patient-partner dyads(800 participants) with diverse backgrounds through the NC Central Cancer Registry rapid case ascertainment (NC CCR RCA). The RCA uses an accelerated process to capture new cases within a week of diagnosis. After receiving a report of localized prostate cancer patients from RCA, we will contact patients' physicians by letter, giving them three weeks to request that a patient not be approached for study inclusion. In one of our studies that RCA facilitated, physicians opted out 81 out of 3400 patients (2.4%) due to patients' severe mental and physical illnesses or insufficient English proficiency. ¹⁰⁸

Study participation data will be provided back to the NC Central Cancer Registry rapid case ascertainment (NC CCR RCA) every six months.

After the 3 week window, we will mail study introduction, a brochure, an opt out letter and informed consent information to potential participants. Then we will call within two weeks to assess interest in participating, answer questions, and screen for eligibility. We will use the same procedure to screen partners' eligibility after eligible patients give permission for us to contact their partner. We will obtain informed consent from eligible patients and partners *via* telephone.

After consented patients and partners independently complete the baseline survey via telephone, dyads will be randomized to PERC or the control group using a 1:1 ratio. v will generate allocation sequences by computerized randomization with randomly permuted blocks of random sizes. The Co-I statistician ([name]) will generate allocation sequences by computerized randomization with randomly permuted blocks of random sizes. *Randomization will be stratified by type of treatment*, surgery or radiation with or without hormonal therapy. Randomization will be centrally allocated using REDCap to ensure the security of randomization lists from all study personnel. After randomization, dyads will be informed of group assignment via email, mailer and/or telephone (the communication

methods participants prefer) and study activities and invited to start either the PERC or NCI program.

Research staff (see **Data Management** for details) will be blinded to the randomization and collect all data using telephone survey at baseline (upon enrollment) and at 4, 8, and 12 months post-T1. Telephone surveys (recorded) will be scripted with simultaneous online data entry into REDCap database system, a secure database for data entry and management. It should be noted that password-protected REDCap will be maintained in a secure network environment and comply with UNC security regulations. Only designated research staff and investigators can access the REDCap database.

Participants will receive gift cards in the following amounts at the following timepoints for study activities: \$20 at the completion of the T1 survey; \$30 at the completion of the T2 survey; \$30 at the completion of the T3 survey; \$50 at the completion of the T4 survey. They will also receive a retention gift with an approximate value of \$20 at around 6 months (between T2 and T3) and 10 months (between T3 and T4) after the T1 survey.

The research team will use the new Bank of America gift card system, which allows the study to acquire a gift card for each participant and then load and reload it with varying amounts for the baseline and 3 follow-up surveys. This is a UNC approved system, and no participant identifying data will be shared with any entity outside of study staff. At the discretion of the P.I. and the research staff, we may choose instead to send Amazon or WalMart gift cards, which would be purchased individually by the study. Gift cards will be sent following the completion of each study survey (T1, T2, T3 and T4); retention gifts will be sent at the appropriate time points. The Project Manager will oversee the acquisition and delivery of all gift cards.

We will use a secure online texting service to contact participants in combination with our landline telephone in our research office. We will send generic text message reminders for forthcoming surveys, giftcards, website features and use reminders, and health educator meetings. All Text Magic SMS messages will not contain any PHI and will be sent over password protected UNC Desktop computers that are located in a research office space at UNC School of Nursing that is designated to the project team.

1. Reminder: PERC Survey scheduled with <<STAFF NAME>> on <<DATE>> at <<TIME>>.
2. Thank you for participating in the PERC Study at UNC. Here is the link to your gift card! Contact us at [contact] or [name] if you have any problems claiming your card.
3. Reminder: Claim your gift card, it expires in 30 days
4. Reminder: Send back your gift card receipt to us soon please! Let us know if you have had any problems using your card.
5. Reminder: Log in to the website using your login information at <https://perc.unc.edu/>. Contact the PERC team for help logging in.
6. Reminder: Meet with the Health Educator Signup using the following [link](#) or call us directly to schedule your meeting!
7. Reminder Health Educator meeting scheduled for <<DATE>> at <<TIME>>.
8. Reminder: PERC webinar on <<Day>> at <<Time>>. Use this [link](#) to join.

9. Webinar posted to <<BLANK>> Section of the website! Check it out!
10. Check out the new Discussion Board post here! <https://perc.unc.edu/topics/all>
11. Time to schedule your survey! Let us know what times you are available.

4.4 Expected Risks

The risks of this study are minimal when compared to the knowledge and skills gained for the participants. The proposed study represents a potential benefit to participants for their post-treatment survivorship care. The PERC program has been designed to enhance post-treatment survivorship care by providing patients and partners a tool and specific resources to assess their needs and tailor the care program to their needs.

4.5 Removal of Patients from Protocol

Patients and their partners will become ineligible for further participation in this study if she or he is diagnosed with any type of cancer (eg breast, bowel etc) with the exception of non- melanomatous skin cancer or develops a condition that prevents them from fully participating in study activities such as scheduling and completing surveys, or phone meetings with the Nurse Educator. Participants will also be removed if they decide to withdraw from the study voluntarily.

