5.1 Time and Events Table

	Baseline (T1) PERC & Control	PERC Intervention	4, 8, and 12 months post- baseline (T2, T3, and T4) PERC & Control
Screening	X		
Informed Consent	X		
Randomization	X		
Quality of Life: Functional Assessment of Cancer Treatment (FACT-G): ^{176, 17*}	X	Phone and/or Zoom contact, with Questionnaires at time points	X
Personal factors: Demographics (age, race/ethnicity, income, and education)	X		
Charlson Comorbidity Index_Brief ^{177,178A}	X		X
PROMIS measures of pain, ¹⁷⁹ fatigue, ¹⁸⁰ sleep disturbance ^{181,182}	X		X
PROMIS Cancer Anxiety and Depression measures ^{182,185}	X		X

Couple factors: Relationship quality: Dyadic Adjustment Scale—Brief ^{186-188*}	X		X
Holmes and Rahe Scale	X		X
Cancer-related factors: Type of treatment [#]	X		X
Prostate cancer symptoms: Prostate cancer Index Composite (EPIC) ^{9,189**#}	X		X
Cancer care Financial Toxicity: COST-FACIT	x		x
Appraisal of illness: Appraisal of Illness scales ^{190,191*}	X		X
Coping Resources: Lewis Cancer Self-Efficacy Scale ¹⁹²	X		X
PROMIS Informational, Emotional, instrumental ¹⁹³⁻¹⁹⁵ and social Support ¹⁹⁶	X		X
Adapted Med Diet Screening and physical activity ^{201,202*}	X		X
Measure of Adult Sedentary Time (MOST)	X		X
eHealth Literacy Scale (eHEALS)	X		X
Modified RESIDE Physical Activity Screener	X		X
Perceived Ease of Use and Program Satisfaction ^{203,204*}			
Physical activity logs (health diary)	X		X
PERC web activity (automatic tracking)			X

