7.0 STATISTICAL CONSIDERATIONS

7.1 Study Design

This study is a two-arm, parallel group randomized controlled trial (RCT) to test the efficacy of PERC, a theory-based, couple-focused, tailored mHealth program aimed to improve the QOL of patients with prostate cancer and their partners. After baseline measures (T1, following consent), 250 patient-partner dyads will be randomly assigned to PERC or to control (usual care plus the NCI website) groups. Participants will complete three surveys to assess the short, intermediate, and long-term effects of PERC: at 4 months post-T1 (T2), 8 months post-T1 (T3), and 12 months post-T1 (T4).

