7.3 Data Analysis Plans

A detailed analysis plan will be developed prior to initiating the study; the following is a summary of the proposed plan. Unless otherwise specified, all analyses will include all randomized participants, in the arm to which they are randomized, regardless of the extent of intervention received (intention-to-treat).

Primary Objective: We will compare the longitudinal mean change in overall QOL between groups using analysis of covariance (ANCOVA), conducted using linear mixed models. Data for patients and partners will be fit together in the same model (accounting for within-dyad correlation), which will allow us to readily assess for differential treatment effects between patients and partners. Mixed models will allow for the inclusion of all observed data for all dyads, assuming any missing data are

missing at random. Each model will include fixed effects (separate for patient or partner) for group, month, group-by-month interactions, the baseline value of the outcome scale, baseline treatment type (surgery and radiation +/-hormonal therapy), number of baseline comorbidities, baseline couple relationship quality, baseline family disruptions, age, race/ethnicity, education, income, and number of people supported by the income. These covariates were selected because they are potentially associated with QOL. Models will include random dyad and participant nested within dyad effects to account for within-dyad and within-person correlations between longitudinal responses. For the primary comparison, separately for each participant type, we will first test for any differences between groups across all 3 time points using an appropriately specified 3 degree of freedom linear contrast. Only if this test is significant ($p \leq 0.025$), will we test for group differences at each time point.

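### Section 4.5 does not separate stopping the intervention from stopping outcome collection, so a new cancer can end surveys that the intention-to-treat analysis needs

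*Combined protocol and SAP*

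**What the plan says.** Section 4.5 is the only removal rule in the combined protocol and SAP. Its first trigger is a new diagnosis: "Patients and their partners will become ineligible for further participation in this study if she or he is diagnosed with any type of cancer", with non-melanomatous skin cancer exempt. Its second is a condition that "prevents them from fully participating in study activities such as scheduling and completing surveys, or phone meetings with the Nurse Educator". Its third is voluntary withdrawal. Surveys and educator meetings are named together as study activities. Nothing in the documents describes a person who stops the intervention but stays in outcome follow-up.

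On outcome collection, section 4.3 has blinded staff "collect all data using telephone survey at baseline (upon enrollment) and at 4, 8, and 12 months post-T1". Section 7.1 adds: "Participants will complete three surveys to assess the short, intermediate, and long-term effects of PERC". Section 4.2 gives the same schedule for both arms.

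On analysis, section 7.3 says that, unless otherwise specified, "all analyses will include all randomized participants, in the arm to which they are randomized, regardless of the extent of intervention received". On missing data it says: "Mixed models will allow for the inclusion of all observed data for all dyads, assuming any missing data are" missing at random. The baseline value of the outcome is a covariate, and the primary test is a 3-degree-of-freedom contrast over the three follow-up times.

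**The concern.** An intention-to-treat comparison needs outcomes from people who stop the intervention. Section 4.5 uses one rule for leaving the intervention and for leaving the study. Section 8.4 requires the study to be run exactly as the protocol describes, so staff would have good reason to stop calling a participant after a new cancer diagnosis.

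Such a person may be perfectly able to answer a telephone survey. The missing outcome would then be created by the rule, and by a health event likely to affect quality of life. For someone removed before T2, the model has only baseline information and any data from the other dyad member, so missing at random is doubtful. It is less doubtful after T2, or when the other member stays in follow-up. The detailed analysis plan promised in section 7.3 could add sensitivity analyses, but it cannot recover surveys that were never done.

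The wording also joins patients and partners in the subject of the sentence and then refers to she or he. Patients and partners are tested separately, so a healthy member's primary outcome could be lost because of the other member's diagnosis.

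**Working it through.** **1. The texts side by side.** Section 4.5 ends participation in the study and lists surveys as a study activity. Section 7.3 counts everyone randomized as analysed, whatever intervention they received. Because baseline is a covariate and the outcomes are T2 to T4, a person removed before T2 has no outcome row. That person is included in name but supplies no follow-up outcome.

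**2. The plan's own figures (section 7.2).** Inputs: 125 dyads per group, SD 15, within-person correlation 0.75, two-sided alpha 0.025, loss of up to 7% per 4 months, and effects of 7.5, 7.5 × 0.85 = 6.375 and 7.5 × 0.85² = 5.42 points.

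- Retention is 0.93, 0.93² = 0.8649 and 0.93³ = 0.8044. Attrition is 1 − 0.8044 = 19.6%, which agrees with the stated 20%.
- A repeated-measures model with compound symmetry, monotone loss and a 3-df Wald test gives 94.2% at 4 months and 82.8% at 8 months, matching the stated 94% and 83%.
- The same model gives 66.7% at 12 months against the stated 51%, and 86.7% overall against the stated 90%. It therefore does not reproduce the whole calculation, and only the changes in power below should be used, not the levels.

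**3. Assumed removals.** The documents give no removal rate. Assume that section 4.5 removes an extra share x of 0.5% to 2% of participants per 4 months, on top of the 7%. Retention at follow-up k becomes (0.93 − x)^k. Surveys lost are N × [0.93^k − (0.93 − x)^k], summed over k = 1, 2, 3. With 250 dyads (sections 7.1 and 7.2), N = 500 and the expected total is 500 × (0.93 + 0.8649 + 0.8044) = 1,299.6 surveys.

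| x per 4 months | Lost at T2 + T3 + T4 (N = 500) | Share of 1,299.6 | Overall power |
|---|---|---|---|
| 0 | 0 | 0% | 86.7% |
| 0.5% | 2.5 + 4.6 + 6.5 = 13.6 | 1.0% | 86.5% |
| 1% | 5.0 + 9.3 + 12.8 = 27.1 | 2.1% | 86.2% |
| 2% | 10.0 + 18.4 + 25.4 = 53.8 | 4.1% | 85.8% |
| 4% (2%, both members removed) | 20.0 + 36.4 + 49.7 = 106.1 | 8.2% | 84.8% |

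The T2 column is also the number of people with no outcome row: 2.5 to 10 without doubling. With 400 dyads (sections 1.1, 2.0 and 4.3), multiply the counts by 1.6: 4 to 16 people, and 22 to 86 of about 2,079 surveys.

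The planned analysis adjusts for baseline, which reduces the SD to 15 × √(1 − 0.75²) = 9.92. Overall power then stays above 99.9% in every row. If the removals lie inside the 7% allowance, planned power does not change.

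**4. Bias.** Let q be the share of an arm removed, and D their shortfall in quality of life below the missing-at-random prediction. The arm mean is off by q × D, and the arm difference by q₁D₁ − q₀D₀. With assumed q of 1% to 5% by month 12 and D of 5 to 15 points, an arm mean shifts by 0.01 × 5 = 0.05 to 0.05 × 15 = 0.75 points. With equal q and D in both arms the difference is unbiased. With q of 5% against 2.5% and D = 15, it is off by 0.025 × 15 = 0.375 points, against a planned effect of 7.5.

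**The case against.** Several points on the other side are sound.

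- **Schedule and exception.** A reader might infer that section 4.5 contradicts the survey schedules in sections 4.2 and 7.1. It does not. Those are general schedules, and a removal rule is an ordinary exception to them; otherwise every withdrawal would be a contradiction. The tension is with section 7.3, and it lies in the effect: section 4.5 discards no data already collected and removes nobody for low use of the intervention as such.
- **Wording.** Section 4.5 nowhere says that surveys stop. That is an inference, though a natural one, because participation in the study ends and surveys are named as a study activity.
- **Unavoidable loss.** The condition clause mostly describes people who could not be surveyed anyway. Meetings, like surveys, can be held by telephone, so few people could manage one and not the other. The avoidable loss is mainly among those with a new cancer.
- **Rationale.** Section 3.1 excludes partners with recent cancer so that couples can focus on managing prostate cancer, and section 4.5 may simply carry that restriction forward. This explains who enters. It does not justify ceasing to measure outcomes after randomization. The schedule in section 5.1 already repeats the "Charlson Comorbidity Index_Brief" at T2 to T4, so new illness can be recorded as data.
- **Partial protection.** The model includes baseline quality of life, comorbidities, age and a dyad effect, which makes missing at random more tolerable but does not secure it.

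**Conclusion.** The point holds as a minor one, best described as a cheap improvement. Section 4.5 needs to separate the end of the intervention from the end of outcome collection, and to say what one member's event means for the other.

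The size rests on an assumed removal rate. Under that assumption the power cost is about 1 point or less (86.7% to 85.8%), about 2 points if both members are removed (84.8%), and nil if the removals fall inside the 7% allowance. The case does not depend on power. It rests on avoidable, health-related loss of the primary outcome under a missing-at-random assumption.

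A reader might also infer that the meeting clause removes more people from PERC, which has four educator meetings against one control call, and so biases the comparison. The documents do not support this. They give no removal counts by arm, and few people who can be surveyed would be unable to hold a meeting. Any such imbalance is speculative and probably negligible.

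**What to change.** Reconcile sections 4.5 and 7.3 by amendment:

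- State separately what ends intervention contact, which is for the sponsor to decide, and what ends data collection.
- Continue the T2 to T4 telephone surveys for both dyad members unless consent is withdrawn or the person cannot be interviewed, and keep these data in the primary analysis.
- State that one member's event does not by itself end the other member's surveys.
- Report section 4.5 events by arm.

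The cost is amendment wording and a few more surveys. At the gift-card amounts in section 4.3 (30, 30 and 50 dollars at T2, T3 and T4), 500 participants would cost 2.5 × 30 + 4.64 × 30 + 6.45 × 50 = about 537 dollars at x = 0.5%, and 10 × 30 + 18.4 × 30 + 25.39 × 50 = about 2,122 dollars at x = 2%. For 800 participants, multiply by 1.6: about 860 to 3,400 dollars. Retention gifts and staff time are extra. The downside is slightly more outcome variability from people with new illness.
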